7.8.2.2 Laboratory values of special interest

Hepatic enzyme elevations (potential Hy's law cases):

These are defined as those cases where a combination of all of the following events occurred: any on-treatment value of alanine aminotransferase (ALT) and/or aspartate transaminase (AST) > 3 Upper Limit of Normal (ULN) with total bilirubin \ge 2ULN and alkaline phosphatase (ALKP) < 2 ULN. The events can occur in any order, but must occur within 14 days of the previous event, i.e. the second event must occur within 14 days of the first event, and the third event must occur within 14 days of the second event, etc.

Patients with missing laboratory values for liver enzymes will be excluded from these analyses but will be presented separately in a listing. Tabulations of hepatic enzyme elevations and liver laboratory values (see Section 5.2.2.1 of the CTP), including flags of true DILI (Drug-Induced Liver Injury) cases, are created in accordance with the Food and Drug Administration (FDA) DILI guidance (P09-12413).

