The term AESI relates to any specific AE that has been identified at the project level as being of particular concern for prospective safety monitoring and safety assessment within this trial, e.g. the potential for AEs based on knowledge from other compounds in the same class. AESI need to be reported to the Sponsor's Pharmacovigilance Department within the same timeframe that applies to SAE, see Section 5.2.2.

The following are considered as AESIs:

Hepatic injury

A hepatic injury is defined by the following alterations of hepatic laboratory parameters:

For patients with normal liver function at baseline:

- an elevation of AST and/or ALT ≥3 fold ULN combined with an elevation of total bilirubin ≥2 fold ULN measured in the same blood draw sample, and/or
- marked peak aminotransferase (ALT, and/or AST) elevations ≥10 fold ULN

For patients with impaired function tests at baseline:

- an elevation of transaminase \geq (baseline + 4 x ULN) combined with an elevation of total bilirubin \geq 2 fold ULN measured in the same blood draw sample.
- patients with abnormal liver function tests must have their abnormalities and the etiology documented in detail as baseline conditions. Every effort should be made to explain possible deteriorations of baseline conditions

These lab findings constitute a hepatic injury alert and the patients showing these lab abnormalities need to be followed up according the "DILI checklist" provided in the ISF. In case of clinical symptoms of hepatic injury (icterus, unexplained encephalopathy, unexplained coagulopathy, right upper quadrant abdominal pain, etc.) without lab results (ALT, AST, total bilirubin) available, the investigator should make sure these parameters are analysed, if necessary in an unscheduled blood test. Should the results meet the criteria of hepatic injury alert, the procedures described in the DILI checklist should be followed.

Page 66 of 241

Proprietary confidential information. © 2022 Boehringer Ingelheim International GmbH or one or more of its affiliated companies. All rights reserved.

Dose Limiting Toxicities (DLTs):

• DLTs occurring during the phase Ib escalation cohort will be considered protocol-specified AESI. See section 5.2.3 for DLT definitions. AESI will be reported on the eCRFs/SAE reporting forms, as per the SAE reporting instructions detailed in the 'Adverse Event Reporting' section of the Investigator Site File.

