Urine examination:	pH, glucose, erythrocytes, leukocytes, protein, nitrite will be analyzed by dipstick (semi-quantitative measurements: -, +, ++, ++++, ++++). In case of abnormal findings, further evaluation should be performed and the findings documented.
Other – fasting (only at screening and Day 1 of every cycle)	Blood glucose and HbA1C

Assessment of safety laboratory parameters after approval of Protocol version 10

Blood samples will be collected up to one day prior to the scheduled time points as specified in the Flow Chart and analysed in a laboratory facility at (or close to) the investigational site. Safety laboratory examinations include hematology, biochemistry and electrolytes. See Table 5.2.5: 2 for details. Futher samples may be taken throughout the course of the study when deemed appropriate by the investigator. All analyses are to be performed by the local clinical laboratory.

Table 5.2.5: 2 Safety Laboratory Parameters to be performed after approval of protocol version 10

Category	Test Name
Haematology:	haemoglobin, white blood cell count (WBC), platelets
Biochemistry:	Sodium, potassium, creatinine, aspartate amino transferase (AST), alanine amino transferase (ALT), lactate dehydrogenase, total bilirubin
Other	Blood glucose*

^{*} Glucose may be obtained non-fasting, but in case elevated should be repeated fasting. If Glucose is repeated fasting, only the fasting value should be captured in the eCRF.

Doc. No.: c02304008-15 Trial Protocol Version 12 Page 72 of 241

Proprietary confidential information. © 2022 Boehringer Ingelheim International GmbH or one or more of its affiliated companies. All rights reserved.

If blood sampling at the trial site is not possible, safety lab analyses can be performed at a local lab. The results of the lab tests must be transferred to the investigator who ensures medical review and proper documentation in the eCRF.

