7.8.2 Laboratory data

7.8.2.1 Laboratory data

The analyses of laboratory data will be descriptive in nature and will be based on BI standards (6). The same on-treatment periods as considered for the analysis of AEs will be applied for laboratory values except for that the baseline laboratory value will be included in the 'on-treatment' period. Patients having at least one post-baseline laboratory value will be displayed in the descriptive analyses.

Descriptive statistics, including change from baseline and frequency of patients with transitions relative to the reference range, will be provided. CTCAE grades for applicable laboratory parameters will be calculated according to CTCAE version 4.03 (R10-4848). The following outputs will be presented:

• Worst CTCAE grade experienced during the on-treatment phase.

• Transitions of CTCAE grade from baseline to worst laboratory value, from worst to last laboratory value during the on-treatment phase, and from baseline to last laboratory value.

Patients with missing CTCAE grade at baseline or no baseline value but post baseline values will be displayed in the category "Missing CTCAE grade at baseline". Laboratory values without CTCAE grading will be compared to their reference ranges and frequency tables will be provided for the number of patients within and outside the reference range at baseline and the last measurement on treatment.

Analysis of potentially clinically significant abnormal laboratory values, and handling of CTCAE grade -1 and -9 laboratory parameters, are described in the SOP for "Display and analysis of laboratory data" (6), RD 9.

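### The SAP's potential Hy's law flag cannot be met by a patient with persistently high ALKP, and some such patients also escape the protocol's hepatic-injury rule

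*SAP*

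**What the plan says.** **The flag (SAP 7.8.2.2).** A potential Hy's law case needs "a combination of all of the following events occurred": ALT and/or AST above 3 x ULN, total bilirubin at least 2 x ULN, and "alkaline phosphatase (ALKP) < 2 ULN". The events may come in any order, but each "must occur within 14 days of the previous event". On missing data: "Patients with missing laboratory values for liver enzymes will be excluded from these analyses", although the same sentence adds a separate listing of those patients. The section also plans "Tabulations of hepatic enzyme elevations and liver laboratory values (see Section 5.2.2.1 of the CTP"), with flags for true DILI cases, following a cited regulatory guidance.

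**The AESI (Protocol 5.2.2.1).** With normal baseline liver function, hepatic injury is "an elevation of AST and/or ALT ≥3 fold ULN combined with an elevation of total bilirubin ≥2 fold ULN" in one blood sample, and/or a transaminase of at least 10 x ULN. With abnormal baseline tests, it is a transaminase of at least baseline + 4 x ULN with bilirubin at least 2 x ULN, again in one sample. Neither version mentions ALKP. SAP 7.8.1 reports AESI incidence.

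**Entry and sampling.** Protocol 3.3.2 limits bilirubin (1.5 x ULN) and AST/ALT (2.5 x ULN, or 5 x ULN with liver metastases). ALKP is limited neither there nor in 3.3.3. ALKP is in the safety panel before protocol version 10 (Table 5.2.5:1). The biochemistry line afterwards (Table 5.2.5:2) reads "Sodium, potassium, creatinine, aspartate amino transferase (AST), alanine amino transferase (ALT), lactate dehydrogenase, total bilirubin", without ALKP.

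**The concern.** An ALKP ceiling in a Hy's law rule sets aside patients whose pattern looks obstructive. That reasoning assumes that ALKP reflects the liver. That bone metastases can also raise ALKP is general clinical knowledge rather than a statement in these documents, but the documents make it relevant. Bone scans are scheduled for every patient (Protocol 5.1.2.1), bone progression is part of the primary endpoint (5.1.1.2), and SAP 7.9.4 lists ALKP among the laboratory values to be studied with tumour-cell status as a possible surrogate for PFS or OS. The flag takes no account of baseline ALKP.

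What is at stake is how the potential Hy's law row is read. A zero could mean that no combined rise occurred, or that the patients who had one also had high ALKP. The planned table does not separate the two.

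**Working it through.** No sample size, power or test depends on this point ("The analyses of laboratory data will be descriptive in nature"), and the plan gives no figure to reproduce. The check applies the two combined rules side by side.

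**Inputs**
- SAP flag: ALT/AST > 3, bilirubin >= 2 and ALKP < 2 (all x ULN), each event within 14 days of the previous one (SAP 7.8.2.2).
- AESI, normal baseline: ALT/AST >= 3 and bilirubin >= 2 in one sample, and/or ALT/AST >= 10 (Protocol 5.2.2.1).
- AESI, abnormal baseline: transaminase >= baseline + 4 and bilirubin >= 2 in one sample (Protocol 5.2.2.1).

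**Constructed cases.** The values are illustrative, in multiples of ULN. In each, on-treatment ALT is 4 and bilirubin is 2.5. ALKP is 3 throughout, except in D.

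| Case | Feature | SAP flag | AESI |
|---|---|---|---|
| A | Normal baseline, both rises in one draw | No (3 is not < 2) | Yes (4 >= 3, 2.5 >= 2) |
| B | As A, but the ALT and bilirubin peaks are on draws 7 days apart | No (ALKP) | No (not one sample; 4 < 10) |
| C | Baseline ALT 2, both rises in one draw | No (ALKP) | No (threshold 2 + 4 = 6; 4 < 6) |
| D | As A, but one ALKP value < 2 within the 14-day chain | Yes | Yes |

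In B and C the ALKP condition alone decides the SAP flag. With one ALKP value below 2 x ULN in the chain, both would be flagged: ALT 4 > 3, bilirubin 2.5 >= 2, and in B the gap of 7 days is within 14.

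**How B and C can arise.** Before version 10, safety laboratory tests were weekly in the main flow charts, so two peaks can fall on different draws inside 14 days. In Arm B, and after stopping BI 836845, visits are on Day 1 only from cycle 4, which makes B less likely there. For C, entry at 2.5 x ULN puts the AESI threshold at 2.5 + 4 = 6.5 x ULN. Entry at 5 x ULN with liver metastases puts it at 5 + 4 = 9 x ULN.

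**Later data.** Protocol 2.2 says that data collected after version 10 will be summarised in a revised report. The panel then has no ALKP, so the three-part flag cannot be met unless ALKP is measured outside it. ALT, AST and bilirubin remain, so the AESI combination can still be evaluated. The SAP does not say whether a missing ALKP value alone counts as a missing liver enzyme.

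**The case against.** A reader might infer that combined rises in high-ALKP patients are never flagged anywhere. The documents do not support that. The AESI has no ALKP condition, triggers an alert with checklist follow-up, and is reported within 24 hours. Its incidence is tabulated, and SAP 7.8.2.2 itself points to that definition. Case A is therefore caught, and so is a transaminase of at least 10 x ULN from a normal baseline.

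Further points on the other side stand:
- Only persistently high ALKP blocks the flag, since one lower value in the chain satisfies it (case D).
- Patients excluded for missing values are still listed.
- The SAP is dated 28 September 2017 and protocol version 10 is dated 13 September 2019, so the reduced panel is not an error in the SAP as written.
- Surveillance during the trial rests on the AESI process, not on an end-of-trial table. The point concerns reporting, not detection in real time.
- Bone metastases are not an entry requirement, and no proportion with bone disease is given.
- Whether the ALKP condition follows the cited guidance cannot be settled from these documents.

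CTCAE grade and shift tables (SAP 7.8.2.1) and the hepatic event category (SAP 7.8.1) are additional nets. However, the grade tables take one parameter at a time and the category works on event terms. Neither links ALT/AST to bilirubin across draws, so cases B and C remain open.

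**Conclusion.** The point holds in a limited form. A patient whose ALKP stays at or above 2 x ULN cannot enter the potential Hy's law row. High-ALKP patients with rises on separate draws within 14 days, or with abnormal baseline transaminases below baseline + 4 x ULN, are missed by both combined rules. This follows from the wording of the two rules and needs no assumption about frequency.

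The size cannot be computed. A reader might assume that 20 to 50% of patients have ALKP of at least 2 x ULN and conclude that the flag captures at most 50 to 80% of combined rises (100 - 50 and 100 - 20). The documents give no such prevalence. The step also assumes that ALKP is unrelated to having a combined rise, and it ignores the cases that the AESI catches.

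This is an inexpensive improvement to one descriptive table. It is not evidence that liver safety goes unmonitored, nor that the present definition is wrong as one category among others.

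**What to change.** In SAP 7.8.2.2:
- Add a row for ALT/AST above 3 x ULN with bilirubin at least 2 x ULN under the same 14-day rule, irrespective of ALKP.
- Split it by ALKP below 2 x ULN, at least 2 x ULN, and missing. Keep the present potential Hy's law definition as the first sub-row.
- State that a patient is not excluded because ALKP alone is missing. This also lets the row be used for the revised report on data collected after ALKP left the panel.
- Say which ALKP value decides the split. Assigning every patient who meets the present definition to the first sub-row keeps that count unchanged. With ALKP as the middle event, the present chain can span 14 + 14 = 28 days between the ALT/AST and bilirubin values, so count such patients in the overall row too.

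The cost is a few lines of SAP text and extra rows in one table, with no new data collection. The downside is that a few cholestatic or liver-metastasis cases will appear and need medical review.

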7.8.3 Vital signs

Only descriptive statistics are planned for this section of the report.

7.8.4 ECG

All ECG analyses will be performed using the ECG Set, except those concerning the relationship between plasma concentrations and ECG endpoints which will be based on the ECG-PK set.

Descriptive analyses (separate analysis of first and second parts)

Descriptive analyses of continuous and categorical endpoints will be performed. The QTcB interval as well as the percentage changes for PR interval and QRS complex will only be displayed in Listings (Appendix 16.2.8 of the CTR)

Absolute values and change from baseline in QTcF interval, QT interval, heart rate, PR interval, and QRS complex will be summarized descriptively by initial treatment, cycle, day and planned time.

Frequency tables will be provided for all categorical endpoints including notable findings and qualitative ECG assessments. Frequencies of the increases in QTcF and QT intervals above

thresholds such as 450 msec, 480 msec, and 500 msec between baseline and on-treatment values will be displayed in two-way shift tables by initial treatment.

Patients in the TS who have notable findings but are excluded from the ECG Set will be listed in separate listings which will be presented in Section 15 of the CTR.

Additional statistical analyses will be performed as described in the following.

Repeated measures analyses (Phase II part only)

The following analyses will only include the ECG interval data of both arms of the Phase II part.

The endpoint 'change in QTcF interval between baseline and on-treatment' will be analysed by a linear mixed-effects model for repeated measures (MMRM). This model will include the fixed, categorical effects of 'treatment' and 'timepoint', the 'treatment-by- timepoint' interaction, as well as the continuous, fixed covariate 'baseline' and the 'baseline-by-timepoint' interaction. An unstructured covariance structure will be used to model the within-patient measurements. The SAS® procedure MIXED will be used, involving the restricted maximum likelihood estimation method, and the Kenward-Roger method will be applied to adjust standard errors and estimate denominator degrees of freedom. The model is detailed in Section 9.2.2.

Timepoints will only be included as long as evaluable data in 'change in QTcF between baseline and on-treatment' from at least 30 patients are still available in any of the treatment groups. The choice of 30 patients is relatively arbitrary and is conceived as a compromise, i.e. balancing out between precision of the estimates and receiving preliminary information over time on the other hand. The analyses of heart rate, QT, PR and QRS endpoints will be aligned to the respective QTcF analyses.

For the pairwise comparisons of 'xentuzumab + enzalutamide' versus 'enzalutamide', the treatment differences at each timepoint will be estimated by the difference in the corresponding Least-Squares Means (LS Means). Two-sided 90% confidence intervals based on the t-distribution will also be computed. Having estimated the treatment difference at each timepoint by the analysis described above, the timepoint at which the difference is largest will be identified.

This analysis will also be performed using the corresponding endpoints based on the QT interval, heart rate, PR interval and QRS complex, respectively.

The repeated-measures analysis will also be applied to the absolute on-treatment QTcF interval, heart rate, QT interval, PR interval and QRS complex values, respectively. Least squares means of 'treatment-by-timepoint' and two-sided 95% confidence intervals based on the t-distribution will be computed.

Sensitivity analysis

In the model described above, a covariance structure of type 'unstructured' will be used to model the covariances of the within-patient measurements. This model does not consider the particular underlying time structure, being consecutive pairs of within-day measurements (pre- and post-dose measurements approximately 1 hour apart) separated by one (or more) week(s). To account for this particular time structure, a modified covariance structure will be used in the sensitivity analysis: A two-by-two unstructured covariance matrix will be used to

model the within-patient measurements on each day (pre- and post-dose measurements). A second two-by-two unstructured covariance matrix will be used to model the within-patient measurements between days; this matrix will be the same for all combinations of days. Hence, in this second analysis the number of necessary covariance parameter estimates will not depend on the number of included timepoints. The sensitivity analysis will be restricted to the endpoints based on the QTcF interval. The model is detailed in Section 9.2.2.

Exposure-response analyses (Phase I and Phase II parts pooled)

The exposure-response analyses will be based on the ECG-PK set. The analyses will include the pooled data of the Phase I and Phase II parts. Patients in the expansion cohort of the Phase I part will be excluded as they are pre-treated with enzalutamide. Data of patients receiving enzalutamide alone (Phase II part) will be included with xentuzumab plasma concentrations set to zero (see R17-0553).

Pairs of xentuzumab plasma concentrations and QTcF changes from baseline that are not time-matched (i.e. a time deviation between PK blood sampling and ECG recording that is not acceptable, see Section 6.6.5) will be excluded from the analyses. When the collecting time of the blood sample or the ECG recording is not available, the pair will also be excluded. The decisions to exclude pairs from the analyses will be made no later than at the final BRPM before DBL (for further details see also Sections 6.3 and 6.6.5).

The relationship between xentuzumab plasma concentrations and QTcF change from baseline will be explored using a random coefficient model including a categorical variable 'treatment' with the two levels 'xentuzumab+enzalutamide' and 'enzalutamide' to estimate the adjusted mean difference between 'xentuzumab + enzalutamide' and 'enzalutamide' in QTcF change from baseline and its 90% confidence interval at clinically relevant plasma concentrations, which are the geometric means of the C1D1_{1h}, C2D8_{1h} and C3D1_{1h} values of the RP2D. The model is detailed in Section 9.2.3. For visualization, plasma concentration against QTcF changes from baseline will be plotted, as well as the (fixed effect) regression line, its 90% confidence interval and the geometric means of C1D1_{1h}, C2D8_{1h} and C3D1_{1h}.

The assumption of a linear relationship will be checked by visual inspection of diagnostic plots (presented in Section 16.1.9.2 of the CTR). If linearity is not given, the concentrations may be log-transformed prior to the analysis.

To inspect (graphically) whether the peaks of the time-profiles for xentuzumab plasma concentrations and QTcF interval changes from baseline coincide, figures of the individual time profiles of xentuzumab plasma concentrations and QTcF interval changes from baseline will be generated for each patient (presented in Appendix 16.1.9.2 of the CTR), as well as for the means of the group treated at RP2D/MTD (presented in Section 15 of the CTR). Mean time profiles from the patients treated with enzalutamide alone will be displayed as well.

These analyses will also be performed using the corresponding endpoints based on the QT interval and heart rate.

Furthermore, a first sensitivity analysis will be performed using the random coefficient model described above including the categorical effect 'day', and a second sensitivity analysis will be done including the categorical effect 'time' with the two levels pre- and post-dose, instead. These analyses will only be applied to the QTcF changes from baseline.

Appropriateness of QT interval correction methods for heart rate

To evaluate the appropriateness of the heart rate correction methods of QT interval, slopes of the relationship of QT, QTcF, and QTcB interval versus RR interval (values log-transformed using the natural logarithm) will be estimated by applying a random coefficient model (see Section 9.2.4) separately for the treatments 'xentuzumab+enzalutamide' and 'enzalutamide'. These analyses will be based on the on-treatment single ECGs (i.e. three values per time point). A table of the resulting (fixed effect) slopes will be displayed together with two-sided 95% confidence intervals in Appendix 16.1.9.2 of the CTR.

